1.4 Pre-clinical studies of pEVAC-PS

1.5. Dose Rationale

The CE-marked PharmaJet Tropis intradermal (ID) delivery of DNA has demonstrated to be highly effective at reducing the dose required for anti-viral responses in several different systems. An adaptive dose escalation regime follows to discover the lowest dose of DNA which will produce an effective immune response when delivered intradermally, with potential doses of 1.2mg, 0.8mg, 0.4mg and 0.2mg.

Objective	Outcome measure			
Primary To assess the safety and reactogenicity of a new pan-Sarbeco Coronavirus DNA candidate vaccine pEVAC-PS in a boosting regime in healthy volunteers.	 a) Occurrence of solicited local reactogenicity signs and symptoms for 7 days following vaccination; b) Occurrence of solicited systemic reactogenicity signs and symptoms for 7 days following vaccination; c) Occurrence of unsolicited adverse events (AEs) for 28 days following vaccination; d) Change from baseline for safety laboratory measures and; e) Occurrence of disease enhancement episodes 			
Secondary To assess the humoral immunogenicity of pEVAC-PS when administered to healthy volunteers as a booster vaccine, through the analysis of SARS-CoV and SARS-CoV-2 RBD antibody titres. To assess the humoral immunogenicity of the candidate vaccine pEVAC-PS at 28 days (4 weeks) after 2 doses of pEVAC-PS have been administered 28 days apart, given by needle-free technology (PharmaJet); both administered in split doses, left and right deltoids (when >0.2mg)	 a) Serology: receptor binding domain (RBD) responses in the majority of vaccinees per group for SARS-CoV and SARS-CoV-2 			
Secondary Assess optimum dosing of candidate vaccine pEVAC-PS	a) Compare dose tolerability and results of immunogenicity of up to four different doses of PharmaJet ID			

2. Objectives and Endpoints

	administration at 28 days (4 weeks)
	after the second dose of vaccine
Secondary	a) Serology: receptor binding domain
To assess long term (up to 12 months)	(RBD) for SARS-CoV and SARS-
humoral immunogenicity of the candidate	CoV-2 RBD pre and post-
vaccine pEVAC-PS administered by the	immunisation.
needle-free technology (PharmaJet)	
administered as 2 doses (split L&R	
when >0.2mg)	

3. Study Design

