8.2 Statistical analyses

A statistical analysis plan will be produced prior to patient enrolment. This may affect the analyses that can subsequently be done – this will be documented in a revised statistical analysis plan.

Analysis of the safety and immunogenicity endpoints as detailed in **Section 2** will be performed primarily using descriptive statistics. Analysis will be as treated for safety endpoints and per protocol for immunogenicity.

The proportion of patients experiencing each adverse event observed, including biochemical and haematological samples outside the laboratory reference ranges, after each vaccine dose will be calculated and tabulated. For antibody measures means / medians, geometric means and geometric mean fold changes, with 95% confidence intervals will be calculated at each time point, Antibody data will also be described graphically through plotting titres at each time points for each group. The study is not powered for precise comparison of groups but for quantitative measures a non-parametric comparison will be done using either a Mann-Whitney

U test for between-group analyses or, for paired data between time points (e.g. baseline and post vaccination) using Wilcoxon matched pairs test (i.e. comparing numbers that increase vs decrease). If, on a log-scale antibody data are approximately normally distributed then comparison by t-tests and paired t-tests may also be done with adjustment for baseline levels if necessary.

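### Baseline adjustment is optional and has no rule in the between-dose antibody comparison, although the dose groups are not randomised

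*Protocol*

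**What the plan says.** - **Between-group test.** Protocol Section 8.2: "for quantitative measures a non-parametric comparison will be done using either a Mann-Whitney" U test. The variable to be tested (post-vaccination titre or fold change) is not stated.
- **Baseline adjustment.** It appears once, as part of a parametric alternative that opens with the condition "If, on a log-scale antibody data are approximately normally distributed". If that is met, t-tests are allowed as an addition, "with adjustment for baseline levels if necessary". No criterion defines when adjustment is necessary.
- **Status.** The analysis "will be performed primarily using descriptive statistics", and "The study is not powered for precise comparison of groups".
- **Objective served.** The objectives table (Section 2) lists as a secondary outcome: "Compare dose tolerability and results of immunogenicity of up to four different doses", at 28 days after the second dose.
- **Design.** Section 5.5.1 says that volunteers enter groups sequentially and are not randomised. Section 4.1 requires a completed two-dose COVID-19 course, with the last dose at least 84 days earlier and no upper limit. Table 2 schedules an immunology sample for everyone at Day 0 and Day 56.
- **Baseline elsewhere.** Section 8.2 also plans geometric mean fold changes with confidence intervals and paired baseline-to-post tests. Section 3.1.1 defines responders by a 2-fold rise.

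**The concern.** Every participant starts with some SARS-CoV-2 immunity, at a varying time since the last dose. Day 0 RBD titres can therefore differ between people and may predict the Day 56 titre. Randomisation would make any Day 0 difference between dose groups a matter of chance. Here groups fill by order of enrolment, and each stage waits for a review four weeks after the second dose of the stage before, so Day 0 levels may also drift between stages. Section 3.1.1 runs groups 2a and 2b in parallel, which would limit drift between those two, but their allocation is still not random.

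A between-group test that does not adjust for Day 0 carries such a difference into the dose comparison and leaves between-person variation in the error term. At stake are the validity and precision of the immunogenicity part of the dose-comparison objective, with 9 per group at Stage 2 and 9 against 21 if one group is expanded.

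**Working it through.** **1. The plan's own figures.** Section 8.1 gives up to 36 participants and 21 at the selected dose. Both reproduce: 6 + 9 + 9 + 12 = 36 and 9 + 12 = 21. The protocol gives no SD, correlation, effect size or power for the group comparison, so there is no power figure to reproduce.

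**2. Assumptions, none of them from the protocol.** Log titres at Day 0 (x) and Day 56 (y) are bivariate normal with SD 1 and correlation ρ = 0.3, 0.5, 0.7 or 0.8. There are 9 per group and two-sided alpha is 0.05. Data follow y = ρx + e + dose effect, with Var(e) = 1 − ρ² and the same line in both groups. Each setting has 40,000 simulated trials.

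**3. Precision.** ANCOVA reduces residual variance to 1 − ρ²: 0.91, 0.75, 0.51 and 0.36. Power for a true difference of 1 SD, with no baseline imbalance built in:

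| ρ | Mann-Whitney, post titre | t-test, post titre | Mann-Whitney, fold change | ANCOVA |
|---|---|---|---|---|
| 0.3 | 45% | 51% | 34% | 52% |
| 0.5 | 45% | 51% | 45% | 60% |
| 0.7 | 45% | 51% | 67% | 77% |
| 0.8 | 45% | 51% | 84% | 89% |

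About 6 points of the gap between Mann-Whitney and ANCOVA come from leaving ranks (45% to 51%), not from using baseline. Part of that is discreteness: the exact Mann-Whitney test with 9 v 9 has a true size of 4.0%. Baseline itself adds about 1 point at ρ = 0.3 (51% to 52%), 9 at 0.5, 26 at 0.7 and 38 at 0.8. At ρ = 0 ANCOVA has 48%, slightly below the t-test.

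**4. Bias.** Now let one group start 0.75 SD higher at Day 0, with no dose effect. The expected difference between groups is then:

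- post titre: ρ × 0.75 = 0.225, 0.375, 0.525, 0.600 SD
- fold change: (ρ − 1) × 0.75 = −0.525, −0.375, −0.225, −0.150 SD
- ANCOVA: 0

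Rejection rates with no true dose effect:

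| ρ | Mann-Whitney, post titre | Mann-Whitney, fold change | ANCOVA |
|---|---|---|---|
| 0.3 | 6.1% | 11.9% | 5.0% |
| 0.5 | 9.4% | 9.2% | 5.0% |
| 0.7 | 15.0% | 7.5% | 5.0% |
| 0.8 | 18.4% | 6.2% | 5.1% |

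The two unadjusted variables err in opposite directions, and their expected biases are equal in size at ρ = 0.5. Which one misleads more depends on a correlation that nobody knows in advance, and Section 8.2 does not say which one is tested.

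**The case against.** **Baseline is used.** A reader might infer that the Day 0 titre is thrown away. The protocol does not support that: baseline enters the geometric mean fold changes, the paired tests and every 2-fold responder rule. It could also enter the Mann-Whitney test, if that is run on fold change. What stands is that no rule brings baseline into the between-dose test, and that fold change is only a partial remedy (step 4).

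**The statistical analysis plan may settle it.** Section 8 says that a plan will be produced before enrolment and a final one signed off before the final analyses. A reader might infer that the need for adjustment will be judged after looking at open-label results; the protocol does not say so. Still, the protocol itself fixes a covariate-free default and makes adjustment conditional, so this is more than detail left for later.

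**A rank test has merits here.** Section 8.3 assigns half the limit to values below the assay range, so ties at a floor are possible, and the normal model ignores them. The exclusion in Section 4.2 for RBD responses above 2 AUC units may narrow the Day 0 range and lower ρ. Both points stand. They support keeping Mann-Whitney as a sensitivity analysis and reading the high-ρ rows with caution.

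**ANCOVA is not a cure.** The simulation generates data under the ANCOVA model. Unmeasured calendar or assay differences, measurement error at Day 0, or different slopes by dose would leave some bias.

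**Little depends on the test.** It is secondary and descriptive. A reader might infer that escalation decisions are affected; they are not, because Sections 3.1.1 and 8.1 base them on responder counts and tolerability. This limits the severity.

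**Conclusion.** The point holds in a limited form. Section 8.2 makes a covariate-free test on an unnamed variable the between-dose comparison, and leaves baseline adjustment optional and without a criterion, in groups that are not randomised. With an assumed 0.75 SD Day 0 imbalance and 9 v 9, false rejection is about 6% to 18% on post titre and 12% to 6% on fold change as ρ goes from 0.3 to 0.8, against 5% for ANCOVA. The gain in power from baseline runs from almost nothing at ρ = 0.3 to 26 to 38 points at ρ = 0.7 to 0.8, measured against an unadjusted t-test. It would be wrong to credit the whole gap from Mann-Whitney's 45% to baseline.

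All these figures are illustrative. They rest on assumed normality, correlation, imbalance and effect size, and on one common regression line. The argument from bias is stronger than the one from power, because the protocol claims no power for this comparison. Severity is low to moderate.

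**What to change.** In Section 8.2, replace the optional clause ("with adjustment for baseline levels if necessary") with a fixed rule:

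1. Compare dose groups by ANCOVA of log Day 56 titre on dose group with log Day 0 titre as covariate, separately for the SARS-CoV and SARS-CoV-2 RBD titres.
2. Report the baseline-adjusted geometric mean ratio with its 95% CI as a descriptive estimate.
3. Keep the Mann-Whitney test as a sensitivity analysis with its variable named, and rely on it where many values lie at the assay limit.
4. Note in the report that adjustment covers the measured Day 0 titre only, not other differences between groups enrolled at different times.

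The cost is wording in the protocol and the statistical analysis plan. The Day 0 and Day 56 samples are already scheduled for everyone, and sample size and dose decisions do not change. This is a free improvement.

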8.3 Procedure for accounting for missing, unused and spurious data

Missing data will not be imputed. Patients with data missing on any variable required for a given analysis will be excluded from that analysis only. Outliers will be checked but not excluded if data errors are not found. Where results are reported as below or above assay limits a value of half or double the limit will be assigned for quantitative calculations. Antibody data will be logged for presentation or presented on log-scaled axis.

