3.1.1. Immunogenicity endpoints

The adaptive protocol is based on reviews of immunogenicity data which will be made 4 weeks following the second administration of pEVAC-PS (8 weeks following the first dose). The decision for how to proceed will be made on the basis of the proportion of participants within each group who have seroconverted. Seroconversion will be defined as a positive readout from the SARS-CoV and/or SARS-CoV-2 RBD ELISA. The dose used for each group will be classified as either having met immunogenicity target, failed to meet immunogenicity target, or had very poor / no response. Proportions of participant seroconversion will be classed as the following:

Stage 1 – Meets immunogenicity target if 5 or 6 out of 6 participants have at least a 2-fold increase in Ab titre (at 0.2mg) we proceed to Expanded Group 1.

- Stage 2 (Expanded Group 1) if 12/12 participants have a 2-fold increase in Ab titre (at 0.2mg) consider to re-formulate and reduce the dose for a new study.
- Stage 2 (Expanded Group 1) if 10 or more of the 12 participants have at least a 2-fold increase in Ab titre (at 0.2mg) we select 0.2mg as the optimum dose to move forward into a Phase II study.
- Stage 2 (Expanded Group 1) if <=9 participants have a 2-fold increase in Ab titre (at 0.2mg) then a further 9 participants will be recruited to group 2a (0.4) and 2b (0.8mg) each, to be run in parallel.

 - The study will conclude after running groups 2a and 2b.

Stage 1 – Fails to meet immunogenicity target if only 3 or 4 out of 6 participants have at least a 2-fold increase in Ab titre, then we proceed to Groups 2a (0.4mg) and 2b (0.8mg) in parallel.

- Stage 2 if 7-9 or more participants have a 2-fold increase in Ab titre (at 0.4 or 0.8 mg) we expand whichever group has the higher number of responders. If both groups 2a and 2b have 9 responders, we will expand the lower dose.
- Stage 2 if <7 participants have a 2-fold increase in Ab titre (at 0.4 or 0.8 mg) we move to Stage 3 and increase dose to 1.2mg.

Stage 1 – With a poor response, if 2 or less participants out of 6 have a 2-fold increase in Ab titre, we proceed to Groups 2a (0.8mg) and 2b (1.2mg) in parallel.

- Stage 2 if 7-9 participants have a 2-fold increase in Ab titre (at 0.8 or 1.2mg) we expand whichever group has the higher number of responders.
- Stage 2 if <7 participants have a 2-fold increase in Ab titre at 0.8mg and 1.2mg the trial will conclude.

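### The half-or-double substitution factor equals the 2-fold responder threshold, so a constant rather than the measured rise decides response for out-of-range titres

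*Protocol*

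**What the plan says.** Protocol section 8.3 sets one rule for titres outside the assay range: "Where results are reported as below or above assay limits a value of half or double the limit will be assigned for quantitative calculations". It does not limit the rule to descriptive summaries.

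Section 3.1.1 turns titres into dose decisions by counting participants with a 2-fold rise. In Stage 1:

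- "Meets immunogenicity target if 5 or 6 out of 6 participants have at least a 2-fold increase in Ab titre"
- "Fails to meet immunogenicity target if only 3 or 4 out of 6 participants have at least a 2-fold increase in Ab titre"
- poor response "if 2 or less participants out of 6 have a 2-fold increase in Ab titre"

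The same kind of count applies later, with cut-offs of 7 of 9 in Groups 2a and 2b and 10 of 12 in Expanded Group 1. Section 3.1.1 gives no separate handling of out-of-range titres.

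The section also describes the deciding quantity differently. It says "The decision for how to proceed will be made on the basis of the proportion of participants within each group who have seroconverted", and then "Seroconversion will be defined as a positive readout from the SARS-CoV and/or SARS-CoV-2 RBD ELISA". A positive readout and a 2-fold rise are not the same event.

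**The concern.** Assigning half a lower limit is a usual convention for geometric means. Here it meets a responder cut-off with the same factor, 2. For a participant with an out-of-range value, the responder call can then be settled by the constant rather than by the measured change. Crossing a limit through assay noise counts as a response, and a real rise that stays on one side of a limit counts as none.

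The groups have 6, 9 or 12 participants and the counts select the next dose level, so a single call can matter. Out-of-range baselines are plausible, at least for SARS-CoV RBD: participants have no history of SARS-CoV-1 infection, and section 4.2 has an exclusion for RBD responses above 2 AUC units. The protocol does not state where the assay limits lie relative to those baselines.

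**Working it through.** The protocol states no figure to reproduce: section 8.1 gives no power calculation. Inputs from the protocol are the factors 1/2 and 2 (8.3), the 2-fold threshold and the count cut-offs (3.1.1).

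**Step 1, lower limit.** Baseline below L is set to L/2. Any later value of at least L gives a ratio of at least L/(L/2) = 2.0. Example: 0.99L to 1.00L is truly 1.01-fold and is scored 1.00L/0.5L = 2.0.

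**Step 2, upper limit.** A later value above U is set to 2U. Any baseline of at most U gives at least 2U/U = 2.0. Example: 0.99U to 1.01U is truly 1.02-fold and is scored 2U/0.99U = 2.02.

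**Step 3, the opposite error.** If both values lie below L, the ratio is (L/2)/(L/2) = 1.0. So 0.3L to 0.9L, truly 3-fold, is a non-response. A baseline above U is set to 2U, so no later value can show a rise.

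**Step 4, effect on the decision.** One participant turns 4/6 (fails) into 5/6 (meets), or 2/6 (poor) into 3/6 (fails).

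**Step 5, everyone near the limit (assumed).** With no true change and a true titre exactly at L, P(baseline < L) × P(later ≥ L) = 0.5 × 0.5 = 25% are scored responders; uncensored titres give 2.3% at an assay CV of 25%. With the true titre at 0.7L the rule gives 6.8%, and at 0.5L 0.25%, which is below the uncensored rate. The size depends heavily on where the titres sit.

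**Step 6, baselines spread across participants (assumed).** Simulation with 1,000,000 participants per scenario, L = 1 and U = 100. On the natural-log scale the between-person SD is 0.7, the assay SD 0.25 and, where there is a true rise, the response SD 0.3. None of these values is in the protocol. As a check, the uncensored rate at a 3-fold rise is Φ(ln(3/2)/√(2×0.25² + 0.3²)) = Φ(0.405/0.464) = 81%, as simulated. P(at least 5/6) = 6p⁵(1−p) + p⁶, where p is the responder rate.

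| Geometric mean baseline, true rise | Uncensored | L/2 rule (8.3) | L assigned | P(at least 5/6): uncensored / L/2 / L |
|---|---|---|---|---|
| L, none | 2.5% | 8.3% | 0.9% | near 0 for all |
| L, 1.3-fold | 17.7% | 24.1% | 9.3% | 0.001 / 0.004 / 0.000 |
| L, 2-fold | 50.1% | 53.5% | 31.8% | 0.11 / 0.15 / 0.01 |
| L, 3-fold | 81% | 80% | 60% | 0.68 / 0.66 / 0.24 |
| 0.5L, 3-fold | 81.0% | 64.8% | 33% | 0.68 / 0.31 / 0.02 |
| 4L, 2-fold | 49.9% | 50.6% | 49.2% | 0.11 / 0.12 / 0.10 |

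The net shift under 8.3 runs from 24.1 − 17.7 = +6.4 points to 64.8 − 81.0 = −16.2 points, and is about 1 point when baselines centre on 4L. A small net shift can hide offsetting errors: at a baseline of L and a 1.3-fold rise, 9.3% are falsely scored as responders and 2.9% are missed.

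**The case against.** **Scope.** Section 8.3 speaks of quantitative calculations and does not mention the 3.1.1 count. Its natural use is the geometric means and fold changes in 8.2, and the SAP, which is not available here, may treat the responder flag separately. This stands in part. However, a fold rise is a quantitative calculation, the protocol gives no other rule, and it fixes both the factor and the threshold itself. Section 8.1 also lets the investigators use all available information, which softens a mechanical reading of the counts but does not say how out-of-range titres are scored.

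**Crossing may be the intended response.** If the assay limit is also the positivity cut-off, a move from negative to positive meets the seroconversion definition without any substitution. That is a fair point. It shows that the two definitions in 3.1.1 need reconciling; it does not justify leaving the choice to a constant in 8.3.

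**Inflation is not shown.** A reader might infer from steps 1 and 2 that the rule inflates the responder count. The documents do not support this. Step 3 works the other way, and the sign depends on limits and baselines that are not given. A reader might also combine the two antigens to reach 1 − 0.75² = 44% false responders. That puts every participant exactly at L for both antigens with independent errors, although all have had two SARS-CoV-2 vaccine doses. Even then P(at least 5/6) is only 0.06. The upper-limit case is exact algebra, but nothing in the protocol shows how often it would arise.

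**Simply assigning L is not a clean cure.** This stands. At a 3-fold rise with baselines centred on L, P(at least 5/6) is 0.24 with L assigned, against 0.66 under the present rule and 0.68 uncensored.

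**Conclusion.** The concern holds in this form: for titres outside the assay range, the 3.1.1 responder call is fixed by the substitution constant. This follows exactly from the stated factor and threshold and needs no assumption beyond 8.3 applying to the count, as its wording implies.

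Whether the rule over- or under-counts overall cannot be settled from the protocol. Under the assumed spread of baselines the shift ranged from about +6 to about −16 percentage points. With no true rise in that setting, P(at least 5/6) stays near 0 under either rule, so a wholly inactive dose passing Stage 1 is not the main risk. The risk is that one or two calls at a limit move a small group across a branch point in either direction. The point should be settled before the first immunogenicity review.

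**What to change.** In 8.3, state that substituted values alone do not decide responder status under 3.1.1, and add:

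- **Above U:** re-assay the serum at a further dilution instead of assigning 2U.
- **Baseline below L:** prespecify the responder criterion. Report the count under both conventions, L/2 and L (the latter requiring at least 2L after vaccination), and flag any dose decision that differs between them. State that requiring 2L lowers sensitivity for true responders with undetectable baselines.
- **Descriptive summaries:** keep half-limit values for geometric means.
- **Section 3.1.1:** reconcile the 2-fold count with the positive-readout definition of seroconversion, so that one rule drives the decision.

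The cost is a few re-assays of sera that section 5.8.3 already keeps in frozen storage, one extra count at each review, and a short text change. Reporting both counts does not remove the uncertainty below L; it shows when a decision depends on it.

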8.4 Procedures for reporting any deviations from the original statistical plan

These will be documented and reasons for changes given

9. Data Handling

9.1 Data collection tools and source document identification

9.1.1 Source Data

ICH E6 section 1.51, defines source data as "All information in original records and certified copies of original records or clinical findings, observations, or other activities in a clinical trial necessary for the reconstruction and evaluation of the trial. Source data are contained in source documents (original records or certified copies)."

Source Data Verification (SDV) will be undertaken as part of the monitoring activities for the trial. See **Section 10.1** for further details.

